7.5. MODIFIED FULL ANALYSIS SET

The modified full analysis set (mFAS) will include all subjects in the FAS who have at least one on-treatment measurement (excluding late baseline visit data) for the 12-minute walk distance (12MWD). This set is to be used for supplementary analyses.

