8.1.3 Analysis Populations

Screened Set	All subjects who sign the informed consent form.
Randomized Set	All subjects who are randomized.
Full Analysis Set (FAS)	All randomized subjects who receive at least one dose of study treatment.
Modified Analysis Set	All randomized subjects who receive at least one dose of study treatment and at least one on-treatment measurement*.
Safety Set	All subjects who receive at least one dose of study treatment.
Per protocol (PP) Set	All subjects in the FAS who do not violate inclusion or exclusion criteria and/or deviate from the protocol, in a way that could influence their efficacy assessment. Subjects who walk more than 1000m in the Baseline 12MWT will also be excluded from the set.
PK Set	All subjects in the FAS who receive REN001 and have at least 1 evaluable post-dose PK measurement (even if this is <Level of Quantification (LOQ)).

* For the primary endpoint this will be 12MWD

The FAS will be used for reporting demographic and baseline characteristic data, and as the primary analysis population for efficacy. Subjects will be analyzed by planned treatment. The PP set will be used for sensitivity analyses of the primary and secondary endpoints.

All safety analyses will be based upon the Safety Set. Subjects will be analyzed by the treatment received.

After all the data have been verified/coded/entered into the database, a review will be performed. The purpose of this review will be to define the analysis populations. The review will also check the quality of the data, identify outliers, and make decisions on how to deal with any data issues (e.g., missing values, withdrawals, protocol

deviations). After the pre-analysis review, resolution of all issues and documentation of all decisions, the database will be locked.

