Unless stated otherwise, an on-treatment measurement will be any measurement collected (including scheduled and unscheduled visits) up to the date of last dose plus one day for safety endpoints and plus seven days for efficacy endpoints. Drug interruptions will not be considered, i.e., data will not be excluded during a drug interruption if the subject resumes study treatment.

In by-visit summary tables, the baseline will be summarized using all available data, but also for each visit using only the baseline data from subjects with available data at the visit; hence the mean change from baseline will equal the mean observed visit value – mean baseline value.

Throughout this document ‘change from baseline’ refers to the actual change from baseline (i.e., observed visit value – baseline value).

Summary tables will be split by treatment group (REN001 100 mg and placebo). Baseline summary tables (disposition, demography, baseline characteristics, medical history and prior medications) will also include an overall summary.

All data for randomized subjects, who receive at least one dose of study medication, will be listed. For screen failure subjects only disposition (including reason for screen failure), demographics and protocol deviations will be listed.

Data listings will be ordered by treatment group and subject. A subject’s mutational genotype (m.3243A>G, m.8344A>G, mt deletion or Other) will be identified on the listings. Data listings will present study days in addition to dates, where study day is derived as per SDTM guidelines i.e., study day is derived as (assessment date – first day of dosing +1) after the start of dosing and as (assessment date – first day of dosing) before the start of dosing. Hence, the first day of dosing will be identified as Study Day 1.

All statistical analyses will be performed using SAS® (Version 9.4 or higher, SAS Institute Inc., Cary, NC, USA).

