10.1.4. Sensitivity Analyses

The following sensitivity analyses will be performed for the primary endpoint with the FAS:

1. Pattern mixture multiple imputation. This will assume that missing data after treatment discontinuation (i.e., date of last dose of study drug) in either treatment group will be assumed to follow a similar trajectory to those in the placebo group. All missing data including missing data due to intercurrent events will be handled using the same methodology described in [Section 8.3.1](#), the MNAR statement together with the MODEL option from the SAS[®] MI procedure will be used to impute missing data based on the placebo treatment group only.

The same model used for the primary analysis will then be applied to the imputed datasets.

For this sensitivity analysis the data including imputed values, and associated change from baseline and percent change from baseline values will be summarized by visit.

2. Tipping point analysis (O’Kelly 2014). This will assume that the missing values at least possibly related to a subject’s PMM deviate by a certain amount, delta, in a worsening direction. All values will be imputed using multiple imputation (i.e., MAR) and then a sequential series of analyses will be performed where a value delta is subtracted from the imputed values for those possibly related to PMM. The range of delta will be applied in increments of 5. If it exists, the delta that turns the conclusion from favouring one group to favouring the other is called the tipping point.

A check will be made to ensure the adjusted imputed value is plausible i.e., ≥ 0 , and if not, the value will be fixed at zero. The same model used for the primary analysis will then be applied to the imputed datasets.

For this analysis, a table giving results for each progressively increasing delta value will be produced for Weeks 12 and 24. A forest plot of the estimate of the treatment difference and associated 95% confidence interval for each delta incremental value will also be presented for Weeks 12 and 24.

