2. Tipping point analysis. This method assumes that the missing values at least possibly related to a subject's PMM deviate a certain amount, delta, in a worsening direction. Missing data will be imputed using multiple imputation (i.e., MAR) as defined in [Section 8.3.1](#); then a sequential series of analyses will be performed where a value delta is added to the imputed values for those related to PMM. The delta will be applied in increments of 5 which is equivalent to half a standard deviation based on a US population. If it exists, the delta that turns the conclusion from favouring one group to favouring the other is called the tipping point.

A check will be made to ensure the adjusted imputed value is plausible i.e., ≥ 30.3 and ≤ 83.6 , and if not, the value will be fixed at either 30.3 or 83.6 respectively. The same model used for the main analysis above will then be applied to the imputed datasets.

For this analysis, a table giving results for each progressively increasing delta value will be produced for each visit. A forest plot of the estimate of the treatment difference and associated 95% confidence interval for each delta incremental value will also be presented for each visit.

3. ANCOVA. If the primary analysis model described above does not converge then ANCOVA will be used as the main analysis. However, if the model does converge then as an additional sensitivity analysis the ANCOVA approach will be used to analyse the change from baseline at each post-baseline visit separately. The ANCOVA model will include a fixed term for treatment and the mutation stratification factor, continuous baseline score and continuous baseline distance walked during the 12MWT as covariates.

Supplementary Analyses

The following supplementary analyses will be performed:

1. Per protocol analysis. The analysis will be repeated for the PP analysis set.
2. While on-treatment strategy. Only on-treatment values (up to 7 days after the subject's last dose of study drug) will be considered for analysis; consequently, only subjects in the mFAS will be included. This analysis will take the last value prior to discontinuation of study treatment.

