The last on-treatment change from baseline will be analysed using an ANCOVA. The model will include a fixed term for treatment and the mutation stratification factor, continuous baseline score and continuous baseline distance walked during the 12MWT as covariates. The treatment comparison will be estimated, along with its standard error, 95% confidence interval and associated p-value.

3. Treatment period restricted analysis. On-treatment values will be analysed for the mFAS. The same model used for the main analysis will be applied. All missing data will be assumed MAR and predicted from the MMRM model without multiple imputation.
4. Non-parametric analysis. All missing data including missing data due to intercurrent events will be handled using the same methodology described in Section 8.3.1. A Hodges-Lehmann estimate ('Interval midpoint') and asymptotic standard error will be calculated for change from baseline, taking account of the variables:
 - a. Stratification mutation factor
 - b. Categorical baseline T-score (≤ 60 and > 60)

The estimates will then be combined across the imputations to give a pooled estimate of the treatment effect which will be presented together with the asymptotic standard error, 95% confidence interval and associated p-value.

As for the primary endpoint, the impact of all subgroups (specified in [Section 8.5](#)) will also be investigated descriptively. Summaries will be presented by subgroup and the imputed datasets generated for the main analysis will be analysed by subgroup using the main analysis model. A forest plot of the estimate of the treatment difference and associated 95% confidence interval for each subgroup will be presented for Weeks 12 and 24 only.

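### The PROMIS on-treatment analyses use a modified analysis set defined by the walk test, so a few subjects with valid on-treatment PROMIS scores are excluded

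*SAP*

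**What the plan says.** **The set.** SAP 7.5 has one mFAS for all endpoints: "subjects in the FAS who have at least one on-treatment measurement (excluding late baseline visit data) for the 12-minute walk distance". The corresponding set in Protocol 8.1.3 requires at least one on-treatment measurement without naming it, and a footnote adds "For the primary endpoint this will be 12MWD". SAP Section 14, which lists changes from the protocol, does not mention the narrower definition.

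**Its use for PROMIS.** In SAP 10.2.1 the while on-treatment analysis says "consequently, only subjects in the mFAS will be included", and the treatment period restricted analysis says "On-treatment values will be analysed for the mFAS".

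**The schedules.** After baseline, PROMIS is collected at Weeks 4, 12, 18 and 24 (SAP 4.2) and the walk at Weeks 12 and 24 (SAP 4.1). Both are also on the Early Termination list. For subjects who cannot attend the full Early Termination visit, Protocol 6.8 marks the assessments to be pursued with an asterisk. PROMIS has one and the 12MWT does not.

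**The cut-off.** SAP 8.2 counts a measurement as on-treatment up to the date of last dose "plus one day for safety endpoints and plus seven days for efficacy endpoints". The PROMIS while on-treatment paragraph also starts from last dose plus 7 days, but then adds "This analysis will take the last value prior to discontinuation of study treatment".

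**The concern.** A while-on-treatment analysis should use each subject's last on-treatment value of the endpoint being analysed. For the walk, restricting to subjects with an on-treatment walk follows directly. For PROMIS it does not: entry to the analysis depends on a different test with a later first visit. Those removed are early discontinuers, so the exclusion is selective. If early stopping differs by arm, the PROMIS comparison in these two analyses could be biased. The documents do not show in which direction.

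The on-treatment scores of these subjects may also be the only PROMIS data they have after baseline. Protocol 6.9 asks subjects who continue off drug for the MFIS and the 12MWT as a minimum, not for PROMIS. Under the missing-at-random assumption of the treatment period restricted MMRM, a Week 4 score should contribute to the model, and the set definition discards it.

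**Working it through.** **1. The plan's own figure.** The set definition carries no figure, but the sample size supplies the only anchor for drop-out. With a difference of 60 m, SD 125 m, two-sided 5% and 90% power (SAP 3.5), the normal approximation gives n = 2 × (1.960 + 1.282)² × 125² / 60² ≈ 91.2, so 92 per arm. The t-test version gives 92.2, so 93 per arm and 186 in total, as stated. The increase to about 200 leaves 200 − 186 = 14 subjects, or 14 / 200 = 7%, for withdrawals. No discontinuation rate is stated.

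**2. Who is excluded.** Let L be the study day of last dose. A measurement is on-treatment if its day is at most L + 7 (SAP 8.2). Put the visits on their target days, with PROMIS on Day 28 and the walk on Day 84, and suppose there is no on-treatment walk at Early Termination.

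- The Week 4 PROMIS is on-treatment if 28 ≤ L + 7, so L ≥ 21.
- The Week 12 walk is not on-treatment if 84 > L + 7, so L ≤ 76.
- Both hold for L from Day 21 to Day 76: 76 − 21 + 1 = 56 days.

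With the protocol visit windows (Week 4 ± 3 days, Week 12 ± 7 days) the span varies:

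| Week 4 visit | Week 12 visit | L from | L to | Days |
|---|---|---|---|---|
| Day 31 | Day 77 | 24 | 69 | 46 |
| Day 28 | Day 84 | 21 | 76 | 56 |
| Day 25 | Day 91 | 18 | 83 | 66 |

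A Week 12 walk done off drug does not rescue the subject, because it falls more than 7 days after last dose. An Early Termination walk within 7 days of last dose does.

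**3. How many.** Assume that discontinuations are spread evenly over 168 days and that a share s of those stopping in the 56-day span have no on-treatment walk. The number excluded is then 200 × (discontinuation rate) × 56/168 × s.

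| Discontinuation rate | s = 0.25 | s = 0.5 | s = 1 |
|---|---|---|---|
| 5% (10 subjects) | 0.8 | 1.7 | 3.3 |
| 7% (14 subjects) | 1.2 | 2.3 | 4.7 |
| 10% (20 subjects) | 1.7 | 3.3 | 6.7 |
| 20% (40 subjects) | 3.3 | 6.7 | 13.3 |

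The rates other than 7%, the even spread and s are all assumptions. The 7% is an allowance for withdrawals. Stopping study drug can be more frequent, because subjects may remain in the study off drug.

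**4. The two cut-offs.** The only place where the SAP spells out treatment discontinuation as a date is the pattern-mixture analysis of the walk (SAP 10.1.4): "missing data after treatment discontinuation (i.e., date of last dose of study drug". Carried over to PROMIS, this would make a score taken 1 to 7 days after last dose admissible under the first sentence and not selectable under the second. The matching paragraph for the walk in SAP 10.1.5 has no second sentence. Neither reading changes who is in the set.

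**The case against.** The strongest objection is that the Early Termination visit already covers most of these subjects. Protocol 6.8 asks for it as soon as possible after the last dose, the 12MWT is on its list, and SAP 8.2 counts unscheduled measurements too. A reader might infer from the mFAS definition that all early discontinuers with PROMIS data are lost. That is not so, because a subject with a walk within 7 days of last dose stays in. But the visit does not close the gap. The walk is not pursued when the subject cannot come for the full visit, and SAP Section 14 reports that some end-of-treatment PGIC assessments came more than a week after last dose.

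It can also be said that the endpoint-specific reading of the protocol is an inference. The footnote names a measurement for the primary endpoint only, and the protocol plans no on-treatment PROMIS analysis, since PROMIS was exploratory there. That is fair. The case for the change rests mainly on the visit schedules, and the footnote supports it.

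On the cut-off, a reader might infer that Early Termination scores are thrown away, or that the two rules together remove subjects. The text does not establish the first. SAP 8.2, the opening of the paragraph itself, and its model sentence, which refers to the last on-treatment change, all point to last dose plus 7 days. The second is wrong, because the cut-off decides only which score is used. What stands is an ambiguity that two programmers could resolve differently.

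Finally, a subject with only a Week 4 score adds little to the Week 24 estimate in the MMRM. That limits the effect there, but not in the ANCOVA of the last value, where such a subject would count fully.

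**Conclusion.** The point holds within narrow limits. As written, the plan excludes from two supplementary PROMIS analyses those subjects who stop between about Week 4 and Week 12 and have no walk within 7 days of last dose. The size is about 1 to 5 subjects in total at 7% discontinuation. It reaches about 13 only if 20% discontinue and nobody stopping in the span has a timely walk. These figures rest on the assumptions in the working.

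A reader might infer that the secondary-endpoint result is at risk. The documents do not support that. The main PROMIS analysis and the fixed-sequence test use the FAS. The PROMIS sensitivity analyses and the other two supplementary analyses (per protocol and non-parametric) do not use the mFAS. The sample size does not depend on it. The change is desirable and cheap, but not critical. The cut-off wording is a separate and smaller matter of clarity, confined to the while on-treatment analysis.

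**What to change.** 1. In SAP 7.5, or in SAP 10.2.1 for PROMIS alone, define the set for the PROMIS on-treatment analyses as FAS subjects with at least one post-baseline on-treatment PROMIS T-score. Keep the 12MWD-based set for the primary endpoint.
2. In the PROMIS while on-treatment paragraph, replace the sentence on the last value before discontinuation with: *the last on-treatment value (up to 7 days after last dose)*. This agrees with SAP 8.2 and with the primary endpoint's analysis in SAP 10.1.5.

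The cost is SAP wording and one additional population flag. No new data are needed, and no power or sample size figure changes. SAP Section 2 provides for amendments before database lock, so the change should be made before then.

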7.6. PER PROTOCOL ANALYSIS SET

The per protocol (PP) analysis set will include all subjects in the FAS who do not violate inclusion or exclusion criteria and/or deviate from the protocol, in a way that could influence their efficacy assessment. Subjects that meet any of the following criteria will be excluded from this analysis set:

- Walk more than 1000m in the Baseline 12MWT
- Violate any inclusion and/or exclusion criteria that may impact their efficacy assessment

- Receive the wrong study medication
- Discontinue study treatment or are <80% compliant with study medication
- Do not have valid Baseline or Week 24 12MWT assessments i.e., Baseline visit assessment must be prior to first dose and Week 24 visit assessment must be within 7 days of last dose
- Have a change in laboratory result during the study for amphetamines, opiates, cannabinoids, cocaine, barbiturates, benzodiazepines or methadone. The change in result alongside medications the subject received will be reviewed by the Reneo medical team to assess the potential impact on efficacy before excluding
- Inconsistent use of orthotics for the 12MWT at Baseline and Week 24. The change in orthotic use will be reviewed by the Reneo medical team to assess the potential impact on efficacy before excluding.

Precise reasons for excluding subjects from the PP set will be fully defined and documented prior to database lock.

Subjects will be included in their ‘as treated’ treatment group. Note that this will be the same as the randomized treatment because receiving the wrong study medication is a major deviation and reason for exclusion.

7.7. PHARMACOKINETIC ANALYSIS SET

The PK set will include all subjects in the FAS who receive mavodelpar and have at least one evaluable (i.e., not impacted by any important protocol deviations or other events) post-dose PK measurement (even if below the limit of quantification).

7.8. DXA SCAN ANALYSIS SETS

There will be 3 analysis sets for the DXA sub-study:

7.8.1. Screened Scan Analysis Set

The screened scan analysis set will include all subjects who signed the informed consent form for the DXA sub-study and are screened for participation. This analysis set will only be used for the purposes of describing the subject disposition.

7.8.2. Scan Analysis Set

The scan analysis set (ScAS) will include all randomized subjects in the screened scan analysis set who received at least one dose of study drug and who have at least one valid DXA scan (i.e., with parameter measurements). The ScAS will be used for analysis of the DXA data.

7.8.3. Completers Scan Analysis Set

The completers scan analysis set (CScAS) will include all subjects in the ScAS who have both screening and Week 24 valid DXA scans (i.e., with parameter measurements). The CScAS will be used for analysis of the DXA data.

7.9. PROTOCOL DEVIATIONS

Protocol deviations may be identified by site staff, study monitors and medical monitor reviewers. They may also be identified through programmable checks of the data. Site specific protocol deviations will be provided separately from the subject specific protocol deviations.

Protocol deviations will be reviewed on an ongoing basis and categorized by Reneo Pharma Ltd. as either minor or major prior to database lock. Minor deviations are those that do not produce or have the potential to cause harm, do not impact the integrity of the trial, and cannot be avoided due to the subject's schedule or natural events. In contrast, major deviations are events that may have a significant impact on subject's rights or safety, or the integrity of the clinical study data. No subjects will be excluded from the safety set due to protocol deviations.

All protocol deviations will be listed. The number of subjects reporting major deviations will be summarized overall and by deviation category.

8. GENERAL ASPECTS FOR STATISTICAL ANALYSIS

8.1. HYPOTHESIS TESTING

The null (H_0) and alternative (H_1) hypotheses can be expressed as:

$$H_0: m_{REN} = m_{PLA}$$

$$H_1: m_{REN} \neq m_{PLA}$$

where m_{REN} and m_{PLA} are the mavodelpar and Placebo responses, respectively.

8.2. GENERAL METHODS

All statistical testing will be at the 5% level of significance (2-sided) and all point estimates for the comparison between treatment groups will be accompanied by 2-sided 95% confidence intervals. To preserve the Type 1 error a fixed sequence testing procedure will be adopted. Testing will be on the FAS. The order of testing for the primary and secondary endpoints will be:

1. Change from Baseline at Week 24 in distance walked during the 12MWT
2. Change from Baseline at Week 24 in the PROMIS T-score

Continuous variables will be summarized using the number of non-missing observations (n), mean, SD, median, minimum, and maximum. Categorical variables will be summarized using counts and percentages.

Unless otherwise specified, the estimated mean and median for a set of values should be displayed to 1 more decimal place than the original values, and SD should be displayed to 2 more decimal places than the original values. The minimum and maximum should be displayed to the same number of decimal places as the original values. Deviations from this convention may arise to take account of the relevance of the precision (e.g., the distance walked in the 12MWT is reported to the nearest cm, but there is no relevance in presenting the mean to the nearest mm). These deviations from convention will be documented in the relevant analysis sections below.

Percentages will be displayed with 1 decimal place; except percentages will not be presented when the count is zero and 100% will be presented as an integer. Unless stated otherwise, percentages of subjects will be based on the number of subjects with non-missing data in the analysis set used for the presentation.

Baseline will be taken as the last available non-missing assessment prior to study drug administration (Day 1). Although the time of completion is not collected for QoL questionnaires (MFIS, PGIS, PROMIS, SF-36, BPI or WPAI:SHP), any completed on Day 1 will be deemed suitable for baseline as the questionnaires are requested in the protocol to

be completed prior to dosing and, even if after dosing, there is no anticipated effect after a single dose.

Unless stated otherwise, an on-treatment measurement will be any measurement collected (including scheduled and unscheduled visits) up to the date of last dose plus one day for safety endpoints and plus seven days for efficacy endpoints. Drug interruptions will not be considered, i.e., data will not be excluded during a drug interruption if the subject resumes study treatment.

In by-visit summary tables, the baseline will be summarized using all available data, but also for each visit using only the baseline data from subjects with available data at the visit; hence the mean change from baseline will equal the mean observed visit value – mean baseline value.

Throughout this document ‘change from baseline’ refers to the actual change from baseline (i.e., observed visit value – baseline value).

Summary tables will be split by treatment group (REN001 100 mg and placebo). Baseline summary tables (disposition, demography, baseline characteristics, medical history and prior medications) will also include an overall summary.

All data for randomized subjects, who receive at least one dose of study medication, will be listed. For screen failure subjects only disposition (including reason for screen failure), demographics and protocol deviations will be listed.

Data listings will be ordered by treatment group and subject. A subject’s mutational genotype (m.3243A>G, m.8344A>G, mt deletion or Other) will be identified on the listings. Data listings will present study days in addition to dates, where study day is derived as per SDTM guidelines i.e., study day is derived as (assessment date – first day of dosing +1) after the start of dosing and as (assessment date – first day of dosing) before the start of dosing. Hence, the first day of dosing will be identified as Study Day 1.

All statistical analyses will be performed using SAS® (Version 9.4 or higher, SAS Institute Inc., Cary, NC, USA).

